- c) mCLASI activity score ≥ 10 (excluding mucous membrane ulcerations, and diffuse non-inflammatory alopecia)
- d) Not Applicable per Revised Protocol 03 CS (prednisone or equivalent) ≤ 40 mg/day
- e) Meets SLICC 2012 classification criteria for SLE and diagnosed with SLE \geq 24 weeks before the screening visit.
- f) Elevated antinuclear antibodies (ANA) ≥ 1:80 or positive anti-double-stranded deoxyribonucleic acid (dsDNA) (excluding results in the equivocal range) or positive anti-Smith (Sm), as determined by the central laboratory at the screening visit; if initial results for all of these are negative at screening such that a subject would be deemed a screen failure, then 1 retest will be allowed for subjects with a documented history of positive results.
- g) For subjects taking CS, the dose cannot exceed 40 mg/day prednisone or equivalent

4) Medications for Target Disease: SLE Sub-protocol

- a) Requirements for subjects who are receiving chronic therapy with nonsteroidal anti-inflammatory drugs (NSAIDs; including marketed cyclooxygenase-2 inhibitors) are as follows; exceptions or changes may be possible with approval by the Medical Monitor:
 - i. Doses must be stable for 14 days before the screening visit and must remain stable until randomization and throughout the study.

- ii. No more than 1 oral NSAID may be used concurrently during the study and may be combined with topical NSAIDs.
- iii. Use of 1 or more topical NSAIDs is permitted but must follow a stable regimen throughout the study.
- b) Not applicable per Revised Protocol 03 Standard of care that is allowed in this study must have been taken for ≥ 12 weeks before the screening visit and must be at a stable dose for ≥ 8 weeks before the screening visit and remain stable until randomization and throughout study participation. Details for specific medications are as follows:

Antimalarials: chloroquine, HCQ, or quinacrine; monotherapy is permitted. Also see exclusion criteria below regarding HCQ dose limitation and exclusionary screening HCQ levels. Patients on HCQ must have an ophthalmology assessment within 6 months prior to randomization, confirming no findings of HCQ induced retinal toxicity.

Immunosuppressants (combinations of these are NOT permitted):

- i. Azathioprine (maximum 200 mg per day).
- ii. 6-mercaptopurine (6-MP, maximum 1.5 mg/kg per day).

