Randomization will be stratified by immunosuppressant use (yes/no).

Before the study is initiated, each investigator will receive log-in information and directions on how to access the IRT. Study treatment will be dispensed at the study visits as listed in the SoA (Section SLE 1.3).

SLE 6.3 Blinding

Blinded treatment assignments will be managed using IRT. All capsules (branebrutinib 3 mg and PBO) are identical in appearance. Capsules will be supplied in tamper-evident high-density polyethylene (HDPE) bottles with each daily dose made up of either active or PBO capsules (as presented in SLE Table 4). Investigative site staff, Sponsor and designee personnel, and subjects and their families will remain blinded to treatment assignments.

Blinding of treatment assignment is critical to the integrity of this clinical study. However, in the event of a medical emergency or pregnancy in an individual subject in which knowledge of the IP is critical to the subject's management, the blind for that subject may be broken by the investigator. The subject's safety takes priority over any other considerations in determining if a treatment assignment should be unblinded

Before breaking the blind of an individual subject's treatment, the investigator should determine that the unblinded information is necessary, ie, that it will alter the subject's immediate management. In many cases, particularly when the emergency is clearly not related to the IP, the problem may be properly managed by assuming that the subject is receiving active product. It is highly desirable that the decision to unblind treatment assignment be discussed with the Medical Monitor, but the investigator always has ultimate authority for the decision to unblind. The Principal Investigator (PI) should only call in for emergency unblinding AFTER the decision to discontinue the subject has been made.

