Detailed instructions for PK sample collection for the relevant concomitant medications, labeling, processing, storage, shipping, and disposition are provided in the Laboratory Manual. While blood samples will be used for the analysis of HCQ, plasma samples will be analyzed for the other relevant concomitant medications by available validated assays. The results of these post hoc analyses will not be recorded in the clinical study report (CSR).

[figure not shown]
Protocol Amendment No.: 04

Date: 01-Dec-2021

SLE 8.7 Health Economics OR Medical Resource Utilization and Health Economics

Health Economics/Medical Resource Utilization and Health Economics parameters will not be evaluated in this study.

SLE 9 STATISTICAL CONSIDERATIONS

SLE 9.1 Sample Size Determination

Sample size is calculated based on the estimated effect size for the primary endpoint comparison between branebrutinib and PBO treatment groups. The primary endpoint for the SLE sub-protocol is $\geq 50\%$ decrease from baseline mCLASI activity score in subjects with a baseline mCLASI activity score ≥ 10 , at Week 24 and CS (prednisone or equivalent) ≤ 10 mg/day at Week 20 and Week 24.

Estimates for PBO response rates, treatment differences, and common standard deviations were obtained from the published literature. ⁷⁵

Assuming a total sample size of 60 subjects randomized in a blinded fashion in a 3:1 ratio to branebrutinib (45 subjects) or PBO (15 subjects) and a treatment difference of 25% with a PBO response of 30% for mCLASI at Week 24, the 95% CI is expected to exclude 0 (expected 95% CI based on a z-test = 2%, 56%).

Clinical Protocol BMS-986195

SLE 9.2 Populations for Analyses

For purposes of analysis, the following populations are defined:

Population	Description
Enrolled Set	All subjects who sign informed consent.
Full Analysis Set (FAS)	All subjects who were randomized. Following the intent-to-treat principle, subjects will be analyzed according to the treatment assigned at randomization. The FAS will be the primary efficacy analysis population. This is the same as the intent-to-treat population.
Per Protocol Set (PPS):	A subset of the FAS who are compliant with study treatment and who do not have any statistically relevant protocol deviations that may impact the primary efficacy endpoint assessments. The PPS will be analyzed according to the treatment assigned at randomization. The PPS may be a supportive efficacy analysis population.

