Safety Analysis Set	All randomized subjects who receive at least 1 dose of double-blind study treatment. Subjects will be analyzed according to treatment received.
PK	All randomized subjects who receive at least 1 dose of branebrutinib and have any available branebrutinib concentration data. Subjects will be analyzed according to the treatment received during the PK collection.
Biomarker	All randomized subjects who receive at least 1 dose of double-blind study treatment and have at least 1 posttreatment biomarker measurement.

SLE 9.3 Endpoints

The following sections outline the efficacy endpoints for the SLE sub-protocol.

SLE 9.3.1 Primary Endpoint

Proportion of subjects with

• ≥ 50% decrease from baseline mCLASI activity score in subjects with a baseline mCLASI activity score ≥ 10, at Week 24

AND

• CS (prednisone or equivalent) ≤ 10 mg/day at Week 20 and Week 24

SLE 9.3.2 Secondary Endpoints

The following are the secondary efficacy endpoints as defined at Week 24:

- Change from baseline in SLEDAI-2K score
- BICLA response

Protocol Amendment No.: 04

Date: 01-Dec-2021

SLE 9.3.3 Additional Endpoints

The following are the additional efficacy endpoints as defined at Week 24:

- Change from baseline in:
 - Autoantibody titers (ANA, anti-dsDNA)
 - o Complement (C3, C4)
 - High-sensitivity C-reactive protein (hsCRP)
 - o Erythrocyte sedimentation rate (ESR)
 - o SGA of Disease Activity
 - o PGA of Disease Activity
 - Tender joint counts (TJC), swollen joint counts (SJC), and TJC + SJC in subjects with arthritis at baseline
 - o SDI (also change from baseline at the EOT visit, if prior to Week 24)
 - o EQ-5 D-5 L score
 - o PROMIS Fatigue 6 a
 - o Pain NRS

SLE 9.3.4 PK Endpoints

• Concentration values and PK parameters of branebrutinib and metabolites of clinical interest

SLE 9.4 Statistical Analyses

The SAP will be developed and finalized before database lock. Section SLE 9.4.1 provides a summary of planned statistical analyses of the primary and secondary endpoints. Additional and exploratory endpoints will be summarized in a descriptive manner.

SLE 9.4.1 Efficacy Analyses

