Efficacy data will be summarized using the FAS. Data will be summarized using descriptive statistics (n, mean, standard deviation, median, minimum, and maximum), unless otherwise specified, for continuous variables, and frequency distributions (counts and percentages) for categorical variables. Efficacy data will be summarized separately for the SLE sub-protocol and with each sub-protocol combined for variables that are similar among the sub-protocols.

For the SLE sub-protocol, data will be presented for the following treatments:

- Branebrutinib
- PBO

Endpoint	Statistical Analysis Methods
Primary	General Analysis Methodology
	Response rates of branebrutinib compared to PBO for the primary endpoint will be analyzed using a Cochran-Mantel-Haenszel (CMH) test stratified by immunosuppressant use (yes/no). The 95% CI for each treatment group response rate and the difference in response rate for branebrutinib compared to PBO will be provided. If expected cell counts are not sufficient, then Fisher's exact test will be used. Since this sub-protocol is not powered to determine statistical significance, P-values will be added descriptively.
	Supportive Analyses
	Supportive analyses using logistic regression for the primary endpoint may be performed to incorporate additional covariates of interest and to confirm primary analysis results. The odds ratio and the corresponding 95% CI will be provided. Bayesian borrowing to utilize historical controls may also be performed as supportive analyses. Details will be provided in the SAP if needed.
	Imputation Method
	Nonresponder imputation will be used for binary endpoints for subjects who discontinue study treatment early, start a protocol-prohibited

Protocol Amendment No.: 04

Endpoint	Statistical Analysis Methods
	medication/therapy prior to the specified timepoint, or otherwise have missing endpoint data for the specified timepoint.
	Other imputation methods may be considered for sensitivity analyses and will be described in the SAP if used.
Secondary/	General Analysis Methodology
Additional	Response rates of branebrutinib compared to PBO for binary endpoints will be analyzed using a CMH test stratified by immunosuppressant use (yes/no). The 95% CI for each treatment group response rate and the difference in response rate for branebrutinib compared to PBO will be provided. If expected cell counts are not sufficient, then Fisher's exact test will be used.

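### The SLE primary analysis leaves out baseline corticosteroid dose, which the responder definition makes a likely predictor, so it may give up a little precision and leaves chance imbalance uncorrected

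*Combined protocol and SAP*

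**What the plan says.** SLE 9.4.1 has the primary endpoint "analyzed using a Cochran-Mantel-Haenszel (CMH) test stratified by immunosuppressant use (yes/no"). It promises a 95% CI for the difference without giving the method, and falls back on Fisher's exact test if expected counts are too small. SLE 6.2 gives the same single factor: "Randomization will be stratified by immunosuppressant use (yes/no").

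SLE 9.3.1 makes response a two-part condition: at least a 50% fall in mCLASI at Week 24, and "CS (prednisone or equivalent) ≤ 10 mg/day at Week 20 and Week 24". On entry dose, SLE 5.1 (criterion 3g) says: "For subjects taking CS, the dose cannot exceed 40 mg/day prednisone or equivalent". Under criterion 4d CS is not compulsory if an antimalarial or immunosuppressant is taken. SLE 8.1.1.10 makes a subject who is not at or below 10 mg/day by Week 16 a nonresponder, and likewise one who has to go back two or more dose levels during taper.

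Covariates appear only as an option: "Supportive analyses using logistic regression for the primary endpoint may be performed to incorporate additional covariates of interest". None is named, and the output is an odds ratio. On the role of testing, SLE 9.4.1 says: "Since this sub-protocol is not powered to determine statistical significance, P-values will be added descriptively". SLE 9.4 leaves the SAP open until database lock.

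**The concern.** Baseline CS dose is tied to the endpoint by the protocol's own rules. A subject entering at or below 10 mg/day starts out meeting the CS half and has only to stay there. A subject entering above it must taper and hold the lower dose. The primary analysis treats the two alike.

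Two things follow. If one arm happens to receive more high-dose entrants, the estimated difference moves and nothing in the primary analysis moves it back. And if dose is prognostic, the interval is wider than it need be. Because P-values are descriptive, the estimate and its CI carry the result. The continuous endpoints in the same section do get their baseline value as a covariate.

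**Working it through.** **Inputs from SLE 9.1.** "branebrutinib (45 subjects) or PBO (15 subjects) and a treatment difference of 25% with a PBO response of 30"%, so 55% vs 30%, 45 vs 15.

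**The plan's own figure.** SE = √(0.55×0.45/45 + 0.30×0.70/15) = √(0.0055 + 0.0140) = 0.1396. Wald 95% CI = 0.25 ± 1.96×0.1396 = -2.4% to 52.4%. The plan states "expected 95% CI based on a z-test = 2%, 56"%. That interval is centred on 29%, not 25%; it is matched by whole-patient counts of 25/45 vs 4/15 (difference 28.9%, CI 2.2% to 55.6%). This mismatch is a separate matter. Here I use the stated rates. The chance that the CI excludes 0 is then Φ(0.25/0.1396 - 1.96) = 43%.

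**Assumptions.** The protocol supplies neither of the next two quantities. Let q be the share entering above 10 mg/day and k their response rate relative to the rest (the share of skin responses kept after the taper requirement). I take q = 20-50% and k = 30-50%.

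**Size of chance imbalance.** The SD of the between-arm difference in q is √(q(1-q)(1/45 + 1/15)): 11.9 points at q = 20%, 13.7 at 30%, 14.9 at 50%. If high-dose entrants respond 30 points less often (assumed), a one-SD imbalance at q = 30-50% shifts the estimate by 0.137×30 = 4.1 to 0.149×30 = 4.5 points.

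**Large-sample gain.** In each arm p_lo = p/((1-q) + qk) and p_hi = k·p_lo. With d_lo and d_hi the treatment differences at each dose level,

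V_adj = Σ over arms [(1-q)p_lo(1-p_lo) + q·p_hi(1-p_hi)]/n + [(1-q)d_lo² + q·d_hi² - 0.25²]/60.

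- q = 20%, k = 50%: p_lo 0.611 vs 0.333, p_hi 0.306 vs 0.167. V_adj = 0.01887 + 0.00005, SE 0.1376, ratio to 0.1396 = 0.985.
- q = 30%, k = 50%: p_lo 0.647 vs 0.353, p_hi 0.324 vs 0.176. V_adj = 0.01858 + 0.00008, SE 0.1366, ratio 0.978.
- q = 50%, k = 30%: p_lo 0.846 vs 0.462, p_hi 0.254 vs 0.138. V_adj = 0.01581 + 0.00030, SE 0.1269, ratio 0.909.

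**At N = 60.** An extra coefficient costs something in a trial this small, so I simulated it: 6,000 trials per setting, 3:1, blocks of 4 within immunosuppressant stratum, half the subjects on immunosuppressants and that factor not prognostic (all assumed). A linear risk difference adjusted for the stratum alone is compared with one that adds CS >10 mg/day. The last two columns give the chance that the CI lies above 0, stratum only → with CS.

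| q | k | SD ratio | HC1 errors | HC3 errors |
|---|---|---|---|---|
| 20% | 50% | 0.997 | 44.5% → 45.0% | 41.6% → 41.2% |
| 20% | 30% | 0.975 | 44.0% → 45.2% | 40.9% → 41.4% |
| 30% | 50% | 0.988 | 43.8% → 45.2% | 41.0% → 41.4% |
| 30% | 30% | 0.963 | 44.5% → 47.0% | 41.8% → 42.9% |
| 50% | 50% | 0.980 | 45.7% → 46.8% | 42.4% → 42.7% |
| 50% | 30% | 0.928 | 45.8% → 50.3% | 42.2% → 45.7% |
| 30% | 80% | 1.005 | 45.4% → 44.4% | 41.8% → 40.1% |
| 30% | 100% | 1.011 | 45.0% → 44.3% | 41.7% → 40.4% |

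The mean estimate stays at 0.25 within simulation error. Coverage is about 93% with HC1 and 94% with HC3, and barely changes when CS is added. A separate run at q = 50%, k = 30%, measured against a wholly unadjusted analysis, gave SD 0.141 → 0.131 and 45% → 51%. Allowing for simulation error, the range is about 0-8% in SE and 0-6 points with HC1; with HC3 the gain in points is smaller and sometimes absent.

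**The case against.** The planned test is valid. It uses the randomization stratum, and its CI already allows for chance imbalance on average. The sub-protocol says it is not powered and serves development planning. CS is not compulsory, so few subjects may enter above 10 mg/day. Low-dose entrants can also fail the CS half: SLE 2.2 does not prohibit dose increases, and under SLE 6.7.2 rescue after Week 12 makes any subject a nonresponder. With 4 or 5 placebo responders expected (0.30×15 = 4.5), extra terms are not free. All of this stands. It limits the size of the point but does not remove it, because the optional logistic model names no covariate and its odds ratio does not sharpen the risk difference.

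A reader might infer more than the documents support:

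- **That precision is certainly lost, and by a lot.** A correlation of 0.5 between covariates and response would lift the 43% to 54%, but nothing in the protocol supports that value. In the settings above the gain is far smaller and can be slightly negative.
- **That baseline mCLASI belongs in the model equally.** Response is already a percentage change from baseline. With an odds ratio of 0.25 for CS, making mCLASI prognostic as well (0.67 per SD) and adjusting for both gave an SE ratio of 0.979, against 0.984 with mCLASI not prognostic. If it is not prognostic, including it gives back about 1%.
- **That a fuller penalized logistic model is the remedy.** With treatment, stratum, CS and mCLASI (mCLASI not prognostic), a standardized estimate gave no gain in three of four settings in the chance that the CI lies above 0 (44.5% → 42.5%, 45.3% → 44.7%, 46.9% → 45.8%), with a gain only at q = 50%, k = 30% (44.4% → 49.5%). Its SD fell from 0.14 to about 0.13, but the mean estimate shrank from about 0.25 to about 0.23.

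**Conclusion.** The point holds as an improvement to the analysis; the plan is not in error. Baseline CS dose (>10 vs ≤10 mg/day) is a likely predictor by the protocol's own rules, and the primary analysis omits it. The consequence is a possible, probably modest, loss of precision and no correction for imbalance in entry dose between 45 and 15 subjects.

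The 0-8% cut in SE and 0-6 point gain (HC1, against the stratum-adjusted analysis) rest on the assumed 20-50% entering above 10 mg/day and 30-50% of their responses kept. The cost is about 1% in SE if dose is not prognostic. The case rests on baseline CS alone.

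**What to change.** Before unblinding, state in the SAP that the primary estimate is a risk difference with 95% CI adjusted for immunosuppressant stratum and baseline CS (>10 vs ≤10 mg/day, non-users in the lower group). Use a linear or standardized model with those terms and treatment only, and small-sample robust errors such as HC3. Leave baseline mCLASI out.

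Name the sparse-cell fallback in advance. For example, if no placebo subject enters above 10 mg/day, report the risk difference adjusted for stratum alone; at q = 20% that happens with probability 0.8^15 = 3.5%. Keep the CMH test as a sensitivity analysis.

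The cost is SAP wording and one model. No new data are needed, because concomitant CS is already recorded and the dose must be stable from before screening to randomization. The downsides are a slightly less simple primary analysis and a possible SE loss of about 1%. HC3 intervals are also somewhat wider than HC1, with or without the CS term.

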 ≥ 12 weeks prior to randomization and remains stable throughout the study.
 Decrease in dose or discontinuation is permitted for AEs or intolerance.
 - o Leflunomide (20 mg per day).
 - o Mycophenolate mofetil/mycophenolic acid (MMF). Note: Subjects who are receiving MMF may participate in the study only if administered as a maintenance therapy and up to a maximum of 2 g/day (or equivalent); in subjects of African ancestry, 3 g/day (or equivalent) is acceptable.
 - O Dapsone (maximum 100 mg per day).
- e) CS (prednisone or equivalent), as follows:
 - o For subjects taking oral CS as monotherapy, CS must have been taken for ≥ 6 weeks prior to the screening visit at a dose ≥ 7.5 mg/day and ≤ 40 mg/day prednisone (or prednisone equivalent), must be at a stable dose for ≥ 2 weeks prior to the screening visit and remain stable until randomization.
 - For subjects taking oral CS not as monotherapy, the CS dose must be stable for ≥2 weeks before the screening visit, cannot exceed 40 mg/day at screening, and must remain stable until randomization.
 - O Topical and inhaled CS use is permitted but must follow a stable regimen throughout the study and cannot be used on an as-needed basis. Discontinuation of topical steroids should be allowed if lesions/rash resolve completely. Inhaled CS for nonlupus conditions will not count against the maximum CS dose.
 - Subjects are ineligible if they received IM, IA, intrabursal, IV, and modified-release
 CS use within 4 weeks prior to randomization.

5) Other Inclusion Criteria: SLE Sub-protocol

a) Subject re-enrollment (rescreening): This study permits the re-enrollment of a subject who has discontinued the study as a pretreatment (screening) failure (ie, subject has not been randomized/has not been treated). If re-enrolled, the subject must be re-consented.

Clinical Protocol
BMS-986195
IM014029 - SLE
Branebrutinib

SLE 5.2 Exclusion Criteria

An individual who meets any of the following criteria will be excluded from participation in the SLE sub-protocol:

1) General Medical Conditions and History: SLE Sub-protocol

- a) Any major illness/condition or evidence of an unstable clinical condition (eg, renal, hepatic, hematologic, gastrointestinal, endocrine, pulmonary, immunologic, psychiatric) or local active infection/infectious illness that, in the investigator's judgment, will substantially increase the risk to the subject if he or she participates in the study.

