- m) Diquafosol or rebamipide therapy within 4 weeks before randomization or during the study.

- n) For oral CS restrictions, see Section SLE 5.1.
- o) IM, IV, IA, intrabursal, or modified-release CS treatment within 4 weeks prior to randomization or during the study.
- p) Not Applicable per Revised Protocol 01 Treatment with disease-modifying antirheumatic drugs (DMARD) treatments or immunomodulators other than MTX < 8 weeks prior to randomization. The MTX dose must be stable for \geq 12 weeks; new initiation or dose changes during treatment are not permitted.
- q) Not Applicable per Revised Protocol 03 Antimalarial treatments (chloroquine and quinacrine) are permitted but must be stable; new initiation or change in dose during treatment is not permitted. HCQ whole blood concentration > 2 μg/mL (at screening only) is exclusionary. HCQ dose > 400 mg/day, new initiation, or dose increases during treatment are not permitted.
- r) Anti-TNF therapy such as adalimumab, certolizumab, etanercept, golimumab, infliximab, or TNF biosimilars within 3 months prior to randomization or during the study.
- s) **Not applicable per Revised Protocol 03** Administration of a live vaccine within 90 days or an inactivated vaccine within 30 days before randomization; furthermore, live or inactivated vaccines should not be used during treatment or within the 14 days following last dose.
- t) Treatment with anticoagulant or antiplatelet therapies, including aspirin for cardioprotection, within 2 weeks prior to randomization or during the study.
- u) Prior exposure to BTK inhibitors such as ibrutinib, acalabrutinib, or experimental drugs (eg, tirabrutinib, vecabrutinib, zanubrutinib, ARQ-531, fenebrutinib [GDC-0853], or others).
- v) Not applicable per Revised Protocol 03 Treatment with DMARDs (excluding HCQ) or immunomodulators within 4 weeks before randomization; MTX treatment within 12 weeks before randomization or during the study. HCQ whole blood concentration >2 μg/mL (at screening only) is exclusionary. HCQ dose > 400 mg/day, new initiation or dose increases during treatment are not permitted.
- w) Antimalarial treatments (chloroquine, HCQ, and quinacrine) are permitted but must be stable; new initiation or change in dose during treatment is not permitted. HCQ whole blood concentration > 2 μg/mL (at screening only) is exclusionary. HCQ dose > 400 mg/day, new initiation, or dose increases during treatment are not permitted.

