	Topical and inhaled CS	allowed if lesions/rash resolve	Not applicable
		completely. Inhaled CS for	
		nonlupus conditions will not	
		count against the maximum CS	
		dose	
		Must have been taken for ≥ 12	
		weeks before the screening visit	
		and must be at a stable dose for	10 1 10
A	Chl	\geq 8 weeks before the screening	12 weeks if not
Antimalarial drugs	Chloroquine and quinacrine	visit and remain stable until randomization and throughout	continuing as background SOC
		study participation. New	background SOC
		initiation or change in dose	
		during treatment is not permitted	
		Doses of > 400 mg/day are not	
		permitted	12 weeks if not
	Hydroxychloroquine (HCQ)	New initiation or dose increase	continuing as
		during treatment is not	background SOC
		permitted. Whole blood levels at	G 2 2 3
		screening must be $\leq 2 \mu g/mL$ Treatment with anticoagulant or	
		antiplatelet therapies, including	
Anticoagulant or	Anticoagulant or antiplatelet	aspirin for cardioprotection,	
Antiplatelet therapies	therapies, including aspirin	within 2 weeks prior to	2 weeks
	for cardioprotection	randomization or during the	
		study	

Protocol Amendment No.: 04

Date: 01-Dec-2021 78

SLE Table 6 Prohibited and Restricted Medications

Type of Medication	Examples of Medications	Restrictions	Required Washout Period Prior to and Postrandomization
Anti-TNF therapy	Adalimumab, certolizumab, etanercept, golimumab, infliximab, and TNF biosimilars	Prohibited during the study	3 months
Biologics	Rituximab	Prohibited during the study	12 months
	Belimumab	Prohibited during the study	6 months
	Abatacept	Prohibited during the study	6 months
	Other Biologics, including tocilizumab, anakinra		8 weeks
	IVIG	Prohibited during the study	8 weeks
Immunosuppressants (allowed) Note: combinations of immunosuppressants are not allowed	Azathioprine, 6-MP, MTX, leflunomide, MMF	Must have been taken for ≥ 12 weeks before the screening visit and must be at a stable dose for ≥ 8 weeks before the screening visit and remain stable until randomization and throughout study participation. New initiation or dose changes during treatment are not permitted.	12 weeks if not continuing as background SOC, except leflunomide 36 weeks before screening
Immunosuppressants (prohibited)	Cyclosporine, tacrolimus, thalidomide and similar (oral); topical calcineurin inhibitors (tacrolimus, pimecrolimus)	Prohibited during the study	8 weeks
O.I. D.M.D.	Cyclophosphamide	Prohibited during the study	24 weeks

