Other DMARDs (prohibited)	Sulfasalazine and similar	Prohibited during the study	8 weeks
Other DMARDs (allowed)	Dapsone	Must have been taken for ≥ 12 weeks before the screening visit and must be at a stable dose for ≥ 8 weeks before the screening visit and remain stable until randomization and throughout study participation. New initiation or dose changes during treatment are not permitted.	8 weeks, if not continued as background SOC
NSAIDs Ibuprofen, etc		Only 1 oral NSAID is allowed concurrently. Can be combined with 1 or more topical NSAID but must be on a stable regimen	Not allowed on days of study visits until after study assessments are performed
Nonnarcotic analgesics	Acetaminophen	Brief course for up to 7 days allowed	Not applicable
Narcotic analgesics	Oxycodone and, hydrocodone	Prohibited during the study	Not applicable
Immunization against agents other than All live vaccines		Prohibited during the study	90 days before and 28 days after EOT

Protocol Amendment No.: 04

Date: 01-Dec-2021

SLE Table 6 Prohibited and Restricted Medications

Type of Medication	Examples of Medications	Restrictions	Required Washout Period Prior to and Postrandomization
influenza or SARS- CoV-2	Nonlive vaccines unassociated with influenza or SARS-CoV-2		30 days before and 14 days after EOT
Immunization for influenza or SARS-CoV-2	All live vaccines Nonlive vaccines for influenza or SARS-CoV-2	Prohibited during the study Not allowed during the screening period within 30 days prior to randomization During the Treatment and Follow-up Periods, vaccine doses must be given at least 5 days before a study visit. Doses may be given on a study visit day once all protocol-specified procedures are complete.	90 days before and 28 days after EOT
Other treatments	Diquafosol, rebamipide	Prohibited during the study	4 weeks

BTK = Bruton's tyrosine kinase; CS = corticosteroid; DMARD = disease-modifying antirheumatic drug; EOT = end of treatment; IA = intra-articular; IM = intramuscular; IV = intravenous; IVIG = intravenous immunoglobulin; JAK = Janus kinase; MTX = methotrexate; NSAID = nonsteroidal anti-inflammatory drug; SLE = systemic lupus erythematosus; SOC = standard of care; TNF = tumor necrosis factor

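### The SLE nonresponder rule fails skin responders for starting prohibited drugs unrelated to the skin, and leaves unclear whether escalation of allowed background therapy or topical corticosteroid counts as failure

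*Combined protocol and SAP*

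**What the plan says.** **The rule.** SLE 9.4.1 (Primary, Imputation Method) reads "Nonresponder imputation will be used for binary endpoints for subjects who discontinue study treatment early, start a protocol-prohibited", continuing "medication/therapy prior to the specified timepoint, or otherwise have missing endpoint data for the specified timepoint". The synopsis (SLE 1.1) and the secondary-endpoint row of 9.4.1 repeat it. No list of triggering drugs is attached.

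**The endpoint.** SLE 9.3.1 requires a fall of at least 50% in mCLASI at Week 24 together with "CS (prednisone or equivalent) ≤ 10 mg/day at Week 20 and Week 24". Prednisone-equivalent corticosteroid (CS) is the only background therapy that the endpoint restricts.

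**What is prohibited.** SLE Table 6 bars narcotic analgesics ("Oxycodone and, hydrocodone") during the study. SLE 5.2, criterion 5, lists "Treatment with anticoagulant or antiplatelet therapies, including aspirin for cardioprotection, within 2 weeks prior to randomization or during the study" and "Diquafosol or rebamipide therapy within 4 weeks before randomization or during the study"; Table 6 repeats both.

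**What is allowed on conditions.** For allowed immunosuppressants, and for dapsone, Table 6 says "New initiation or dose changes during treatment are not permitted". SLE 5.2 criterion 5w and Table 6 bar starts and dose increases of antimalarials during treatment. On topical steroid, SLE 5.1 criterion 4e says "Topical and inhaled CS use is permitted but must follow a stable regimen throughout the study and cannot be used on an as-needed basis".

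**Separate CS rules.** CS rescue after Week 12 is nonresponse (SLE 6.7.2). So is CS above 10 mg/day at Week 16, or a step back of two or more dose levels during taper (SLE 8.1.1.10). SLE 9.4.1 cites none of these.

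**The concern.** The trigger depends on two words, *start* and *prohibited*, and neither tracks whether a drug can change the skin score.

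It is too wide because many drugs are prohibited for reasons other than lupus activity. Failing subjects who take them removes true responders from both arms and shrinks the difference.

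It is unclear in the other direction. Raising the dose of an allowed drug is not starting one, and Table 6 itself labels these drugs as allowed. A new topical steroid lies within a permitted class. If such a subject is scored as a responder, the endpoint credits the added therapy. Escalation is more likely in subjects who are not improving, so it would tend to raise the placebo rate. That tendency is a judgement; the documents give no data on it.

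Two analysts could therefore classify the same subject differently. BICLA adds to this: SLE 8.1.1.4 defines treatment failure by initiation of nonprotocol treatment, a further term with no definition.

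**Working it through.** **Step 1: trace each event through the text.**

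| Event before Week 24 | Status in the protocol | Reached by the 9.4.1 trigger? | Other route to nonresponse |
|---|---|---|---|
| Start of opioid, anticoagulant/antiplatelet, diquafosol or rebamipide | Prohibited (Table 6; 5.2) | Yes | Not needed; no evident bearing on mCLASI |
| Start of topical calcineurin inhibitor | Prohibited (Table 6) | Yes | Not needed; relevant to skin |
| Dose increase of allowed immunosuppressant or dapsone | Not permitted, in rows labelled allowed (Table 6) | Unclear: not a start | Possibly 6.7.2 (non-prednisone rescue not permitted) or 7.1.1 (noncompliance leads to discontinuation) |
| Dose increase of antimalarial | Not permitted (5.2; Table 6) | Unclear: not a start | As above |
| New or intensified topical CS on lesions | Permitted class; stable regimen required (5.1; Table 6) | Unclear | As above; after Week 12 also 6.7.2, if its CS wording includes topical |
| Oral CS rescue after Week 12, above 10 mg/day at Week 16, or step back of two or more levels | Explicit nonresponse (6.7.2; 8.1.1.10) | Not cross-referenced | Caught by those sections |

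**Step 2: reproduce the design figure.** Inputs from SLE 9.1: 45 vs 15 subjects, placebo 30%, difference 25 points (active 55%), stated 95% CI 2% to 56%. The Wald interval is d ± 1.96 × √[p1(1−p1)/45 + p0(1−p0)/15].

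- At 55% vs 30%: 25.0 ± 1.96 × √(0.0055 + 0.0140) = 25.0 ± 27.4, that is −2.4 to 52.4.
- In whole subjects, 25/45 (55.6%) vs 4/15 (26.7%): 28.9 points, 2.2 to 55.6.

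The stated interval is the second, so it is the baseline for Step 3.

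**Step 3: one reclassified subject.** One active subject is 1/45 = 2.2 points; one placebo subject is 1/15 = 6.7 points.

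| Change from 25/45 vs 4/15 | Difference | 95% CI |
|---|---|---|
| None | 28.9 | 2.2 to 55.6 |
| One active responder set to failure (24/45) | 26.7 | −0.0 to 53.4 |
| One placebo failure counted as responder (5/15) | 22.2 | −5.7 to 50.1 |
| Both | 20.0 | −8.0 to 48.0 |

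**Step 4: expected difference under assumed frequencies.** The documents give none, so q and r are assumptions.

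- A fraction q of responders in both arms fails for an irrelevant drug: difference = (55 − 30)(1 − q). For q = 5%, 10%, 15%: 23.8, 22.5, 21.3 points. At 10% the rates are 49.5% and 27%.
- A fraction r of placebo nonresponders, in that arm only, is counted as response after uncaptured escalation: difference = 55 − (30 + 70r). For r = 5%, 10%, 20%: 21.5, 18.0, 11.0 points.
- Both at 10%: 49.5 − (27 + 7) = 15.5 points.

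**The case against.** A reader might infer that subjects who escalate background therapy are definitely counted as responders. The documents do not support that. The dose changes are not permitted, and nothing says that a change which is not permitted falls outside *prohibited*. SLE 6.7.2 bars rescue other than prednisone, so raising an immunosuppressant for active rash may itself be a prohibited therapy. The same section makes CS rescue after Week 12 nonresponse without repeating the word oral in that sentence. SLE 7.1.1 requires discontinuation for failure to comply, and discontinuation is a trigger. All of this stands, and it limits the second half of the point to an undefined trigger.

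It can also be argued that failing every user of a prohibited drug is a simple, conservative composite that needs no judgement about relevance. That is a legitimate strategy, but simplicity does not make an opioid or an anticoagulant informative about skin disease.

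Other safeguards are weaker. The Per Protocol Set drops deviations that may affect the primary endpoint, but it is only optionally supportive. The SAP is to be finalised before database lock. Its text was not among the material reviewed, so it may already define the trigger; however, 9.4.1 defers only other imputation methods to it.

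Finally, the sub-protocol is not powered for significance and its P-values are descriptive. That lowers the stakes, but it makes the estimate and its interval the result to be read.

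**Conclusion.** The point holds in two parts of unequal strength. As written, the rule fails skin responders who start prohibited drugs with no evident bearing on mCLASI; this follows directly from the text. The rule also does not clearly capture increases in allowed immunosuppressants, dapsone or antimalarials, or new or intensified topical CS on lesions. Such subjects can count as responders on a literal reading, but the documents do not say that they do.

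The size is unknown. Per subject it is 6.7 points in the placebo arm and 2.2 in the active arm, and either single change considered above is enough for the rounded design interval to reach 0. A 10% loss of responders in both arms costs 2.5 points, which is small beside a half-width of about 27. The larger losses for escalation assume that it occurs only on placebo, evades every other rule and still reaches the response threshold; escalation among active subjects would offset part of them. A reader should not take these figures as an estimate of bias in this trial. They show why an ambiguous trigger is worth removing from a 45 vs 15 comparison when the remedy is cheap.

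**What to change.** In SLE 9.4.1, the synopsis and the SAP:

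- Define the trigger as starting, or increasing above the Day 1 dose, any systemic or topical therapy that can affect SLE activity before the Week 24 assessment. List it by class: antimalarials, immunosuppressants, dapsone and other DMARDs, biologics, JAK inhibitors, non-oral CS, and topical CS or topical calcineurin inhibitors on lupus lesions.
- Cross-reference the nonresponder rules in SLE 6.7.2 and 8.1.1.10, and state that oral CS is judged by those rules and the endpoint cap, so that the new trigger does not overlap with them.
- State that other prohibited medications are protocol deviations that do not make a subject a nonresponder. Keep the present any-prohibited-drug rule as a sensitivity analysis.
- Classify medications blind to treatment before database lock.
- Use the same list for treatment failure in BICLA (SLE 8.1.1.4).

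The prohibited set must also be made unambiguous. SLE 5.2 and Table 6 bar anticoagulants during the study, while Master Protocol Table 1 lists dabigatran and rivaroxaban with dose limits. SLE 5.1 allows background methotrexate, while SLE 5.2 criterion 5y names methotrexate treatment during the study as exclusionary. These passages need to be reconciled; which version is right is a clinical decision for the sponsor.

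The cost is wording plus a blinded review of concomitant-medication records already collected on the eCRF. Observed response rates may be slightly lower where escalation occurred.
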